This study is a prospective, randomized, controlled study. The screened qualified subjects were randomly divided into two groups. One group was the control group, receiving clinical routine SSRIs drug treatment combined with blank control method (that is, subjects were allowed to use electronic products to browse the web and watch the news for 1H every day), and the other group was the intervention group, receiving SSRIs drug treatment combined with electronic cognitive training. The whole study lasted 52 weeks.

At each visit, the scale evaluation (cognitive function, psychosocial function evaluation), the level of Alzheimer associated neurofilament protein (AD7C NTP) in urine and the concentration of antidepressants in blood were performed. The investigator quantitatively adjusted the patient's medication regimen (including dose and type) according to the evaluation results and adjusted the cognitive training regimen according to the evaluation results.

2) Drug therapy intervention

The subjects who met the screening criteria did not need cleaning and entered the study directly. Considering that the overall efficacy of various antidepressants is similar, and to maximize the simulation of the actual situation of clinical treatment, SSRIs treatment drugs are used in this study, including fluoxetine, paroxetine, fluvoxamine, sertraline, citalopram and escitalopram. The specific types of drugs are not limited. During the study, the drug dose was quantitatively adjusted according to the results of each visit evaluation combined with the drug concentration.

The researcher will comprehensively evaluate the effectiveness of the treatment according to the above data results, and then make corresponding adjustments according to the treatment plan. If the score reduction rate of the Hamilton Rating Scale for depression (hrsd-17) is >50% and the drug concentration is within the recommended

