no more than 2 times in each training cycle; In addition to the above fixed training, if the training content does not reach 16 items / week, cognitive training in other fields will be randomly pushed; Within each training day, only one cognitive rehabilitation training is arranged for each cognitive field; The difficulty of each cognitive rehabilitation training depends on the last training level of the subject.

Training scheme of the control group: to keep the same electronic use time as that of the intervention group, the subjects in the control group are required to open the electronic products for 60 minutes every day, 4 days a week.

Intervention mode

Tablet computer or mobile phone to be used in this intervention training. The training will take the principles of psychology and cognitive neuroscience as the core, and interactive games as the carrier, covering the cognitive training in six fields: episodic memory, executive function, working memory, processing speed, speech ability and reasoning judgment, to ensure the scientific on the premise of enhancing interest.

According to their own conditions, the subjects can choose to go to the hospital to use the tablet computer provided by the hospital for training within the reserved time or can use their own tablet computer or mobile phone for independent training. The training mode of this intervention is flexible. The subjects can start training on different terminal devices, and the training records can also be updated in real time. The research team will monitor the whole training process.

Research object

Inclusion criteria: 1. written informed consent signed by patients and their families; 2. Age ≥ 60 years; 3. Meet the diagnostic criteria for single or recurrent major depressive disorder in the diagnostic and Statistical Manual of mental disorders Fourth Edition (DSM-V); 4. Currently in the acute phase, the total score of hrds-17 at baseline is ≥ 18 points. 5. There were cognitive impairment symptoms, and the Montreal Cognitive Assessment Scale (MoCA) was < 26 points. 6/ Education level above primary school.

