Exclusion criteria: 1.patients with history of epilepsy or coronary heart disease or other serious unstable physical diseases; 2. Participated in another intervention clinical study in the past 1 month; 3. The following mental diseases have been or are currently diagnosed by DSM-V: organic mental disorder, Alzheimer's disease, secondary dementia caused by other causes, schizophrenia, schizophrenic affective disorder, bipolar disorder, delusional disorder, undefined mental disease, patients with drug abuse history, including alcohol and active drug abuse in the past 12 months, except nicotine; 4.He has been taking antidepressants, mental retardants and other psychiatric drugs for the past 2 weeks; 5. Severe aphasia, visual and hearing impairment, etc. unable to complete the scale evaluation; 6. Pregnant, lactating women or those planning to conceive.

The subject may withdraw from the study for any of the following reasons: the investigator considers that it is best for the subject to terminate the treatment due to safety factors (such as adverse events); The subjects were lost to follow-up; The subject withdrew informed consent. If a subject is lost to follow-up, the staff of the research center shall make every effort to contact the subject and determine the reason for his withdrawal. Follow up examinations must be recorded. When a subject withdraws before completing the study, the reason, date, and final evaluation of withdrawal shall be recorded in the CRF and original documents.

Symptomatic assessment

1) Hamilton Anxiety Rating Scale (HAMA): in the baseline period, at the end of the 2nd, 4th, 8th, 12th, 26th, 38th and 52nd weeks, the rater assessed the anxiety symptoms of the subjects.

2) The Hamilton Rating Scale for depression (hrsd-17): subjects were assessed for depressive symptoms at the end of the baseline period, 2 weekends, 4 weekends, 8 weekends, 12 weekends, 26 weekends, 38 weekends and 52 weekends.

3) The Geriatric Depression Scale (GDS): subjects were evaluated for depressive symptoms at the end of the baseline period, 2 weeks, 4 weeks, 8 weeks, 12 weeks, 26 weeks, 38 weeks, and 52 weeks.

4) Neuropsychiatric Inventory (NPI): subjects were assessed for cognitive function at the end of the baseline period, 2 weeks, 4 weeks, 8 weeks, 12 weeks, 26 weeks, 38 weeks, and 52 weeks.

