5) Activities of daily living (ADL): the cognitive function of the subjects was assessed in the baseline period, 2 weekends, 4 weekends, 8 weekends, 12 weekends, 26 weekends, 38 weekends and 52 weekends.

Safety evaluation

1) Vital signs: the temperature, pulse and blood pressure of the subjects were monitored at the end of the baseline period, 2 weekends, 4 weekends, 8 weekends, 12 weekends, 26 weekends, 38 weekends and 52 weekends.

2) Adverse event report: adverse event records were made on the subjects at the end of the baseline period, the end of the 2nd week, the end of the 4th week, the end of the 8th week, the end of the 12th week, the end of the 26th week, the end of the 38th week and the end of the 52nd week.

3) Treatment Emergent Symptom Scale (TESS): during the baseline period, the subjects were evaluated for side effects at the end of 2 weeks, 4 weeks, 8 weeks, 12 weeks, 26 weeks, 38 weeks, and 52 weeks.

4) Laboratory examination and electrocardiogram: routine blood test, biochemical examination and electrocardiogram examination were conducted at the end of the

screening period, the end of the 4th week, the end of the 12th week, the end of the 38th week and the end of the 52nd week.

Efficacy index

1) Main efficacy indicators:

At the end of the 12th week after treatment, the change value of ADAS cog scale scores of the subjects in the two groups compared with the baseline.

2) Secondary efficacy indicators:

1. At each follow-up point, the change value of ADAS cog scale scores of the two groups compared with the baseline.

2. At each follow-up point, the change value of hrsd-17 score of the subjects in the two groups compared with the baseline;

3. At each follow-up point, the change value of HAMA scale scores of the two groups compared with the baseline.

4. At each follow-up point, the change value of GDS score of the subjects in the two groups compared with the baseline.

5. At each follow-up point, the change value of NPI scale scores of the subjects in the two groups compared with the baseline.

6. At each follow-up point, the change value of ADL scale scores of the subjects in the two groups compared with the baseline.

7. Complete remission rate: the difference in the proportion of patients with a total score of hrds-17 ≤ 7 at each visit point between the two groups.

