8. Effective rate of treatment: the proportion difference between the two groups of subjects in the reduction rate of hrds-17 scale at each visit point and the baseline $\geq 50\%$.

9. Recurrence rate and recurrence time: recurrence is defined as any of the following conditions: the subject meets the DSM-IV diagnostic criteria for depressive episode; The subject was hospitalized again due to depression; After the treatment was effective (ham-d17 score decreased by $\geq 50\%$ compared with the baseline), ham-d17 score increased by more than 30% compared with the baseline at any visit point; During the maintenance treatment period, after the treatment of the subjects is effective or remission, the proportion of relapse and the time of relapse between the two groups at each visit point;

Safety index:

i. Abnormal values of vital signs, laboratory examination and electrocardiogram examination during the study period.

II. Adverse events and adverse reaction reports during the study period.

Basis for determining sample size

According to the main research hypothesis of this study, the effect of comprehensive intervention group on improving patients' cognition is better than that of conventional treatment group. According to the previous similar research results and the expected efficacy hypothesis, the difference between the groups of the study group and the control group in terms of ADAS cog score reduction after 12 weeks of treatment is about 2.2, and the combined standard deviation is 4. Set $\alpha = 0.025$ (one side), $\beta = 0.20$, and set the superiority and effectiveness limit value as 3 in combination with the

previous research and clinical significance, The ratio of the number of cases in the study group to the control group was 1:1. The sample size of the study group was 51 cases, and the sample size of the control group was 51 cases. Considering the 20% rejection rate of similar items, 64 cases need to be included in the study group and the control group.

Statistical analysis methods

Full Analysis Set (FAS): A collection of all randomized cases with valid baseline assessments. FAS is the main analysis set. Secondary efficacy measures were analyzed using only FAS without carry-over.

General principles: Statistical analysis was performed using SAS.9.4 statistical analysis software. P value < 0.05 was statistically significant (unless otherwise specified).

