Efficacy evaluation indicators include HRSD-17, HAMA, GDS, NPI, ADL and other scales. The differences between groups at the visit point relative to the baseline value were analyzed using the same analysis method as the main efficacy indicators. The cumulative complete remission rate, treatment response rate, recurrence rate and other outcome indicators during the study period were compared between groups using the Kaplan-Meier curve, and the COX proportional hazards model was used to evaluate the impact of the intervention while controlling for confounding factors such as disease duration.

Safety analysis: The incidence of adverse events and adverse reactions was tested by chi-square and described in a list.

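### As written, the HAM-D17 recurrence criterion in item 9 needs a score more than 30% above the entry baseline, so a responder who returns fully to entry severity does not meet it

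*Combined protocol and SAP*

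**What the plan says.** The Combined protocol and SAP covers recurrence in two places.

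- **Secondary efficacy indicators, item 9.** Recurrence has three alternative routes, and any one is enough: "recurrence is defined as any of the following conditions: the subject meets the DSM-IV diagnostic criteria for depressive episode", readmission for depression, or a score route. The score route applies once treatment has been effective, meaning a HAM-D17 fall of at least 50% against the baseline. It is met when the "ham-d17 score increased by more than 30% compared with the baseline at any visit point". Item 9 then sets the population and period for the comparison: "During the maintenance treatment period, after the treatment of the subjects is effective or remission".
- **Secondary endpoint analysis.** The "recurrence rate and other outcome indicators during the study period were compared between groups using the Kaplan-Meier curve", with a Cox model alongside.

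Three other places fix the terms. Inclusion criterion 4 (Research object) requires that "the total score of hrds-17 at baseline is ≥ 18 points". Symptomatic assessment, item 2, gives the HRSD-17 schedule: "subjects were assessed for depressive symptoms at the end of the baseline period, 2 weekends, 4 weekends, 8 weekends, 12 weekends, 26 weekends", then weeks 38 and 52. Item 7 defines complete remission through "the difference in the proportion of patients with a total score of hrds-17 ≤ 7 at each visit point".

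**The concern.** A recurrence rule for responders should recognise a patient who improves and then becomes as ill as at entry. The score route names the baseline as its reference, and the plan describes no HRSD-17 baseline other than the acute-phase entry score. Followed as written, the rule asks a responder to become clearly worse than at entry before the score counts.

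The sentence is translated, and an analyst could reasonably suspect that something else was meant. Two analysts could then count different recurrences from the same scores. They could also start the clock at different visits, because item 9 refers to a maintenance period whose start is given nowhere, and the analysis section gives no time origin.

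**Working it through.** The documents give no figure for recurrence, so there is no stated number to reproduce. The sample size concerns ADAS-cog at week 12 and does not bear on this point.

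**Inputs.** B is the baseline HRSD-17 score, at least 18 (inclusion criterion 4). r is the score at response, with r ≤ 0.5B (item 9). The rise must exceed 30% (item 9). Remission is a score of 7 or less (item 7). Two assumptions: HAM-D17 and HRSD-17 are the same scale, and totals are whole numbers.

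**Formulas.** The lowest qualifying score is the smallest whole number above:

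- literal reading: 1.3 × B
- rise measured from the response score: 1.3 × r
- rise in points exceeding 30% of baseline: r + 0.3 × B

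| B | r | Literal | From response score | Points |
|---|---|---|---|---|
| 18 | 9 | 23.4, so 24 | 11.7, so 12 | 14.4, so 15 |
| 24 | 12 | 31.2, so 32 | 15.6, so 16 | 19.2, so 20 |
| 30 | 15 | 39, so 40 | 19.5, so 20 | 24, so 25 |
| 30 | 5 | 39, so 40 | 6.5, so 7 | 14, so 15 |

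**Return to entry severity (score = B).**

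- Literal: B is never above 1.3B, so the patient is never counted.
- From the response score: 1.3r ≤ 0.65B, which is below B, so the patient is always counted.
- Points: r + 0.3B ≤ 0.8B, which is below B, so the patient is always counted.

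Under the literal rule, a patient with baseline 18 who responded at 9 must reach 24. That is 24/9 = 2.67 times the response score and 6 points above entry.

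**Overlap with response and remission.** Neither alternative reading is clean. With B = 30 and r = 5, the second reading counts a score of 7, which is still complete remission. The third counts a score of 15, which is exactly half of 30 and so still a response. Swapping one reading for another is therefore not enough.

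**Clock.** Post-baseline HRSD-17 visits are at weeks 2, 4, 8, 12, 26, 38 and 52. If maintenance starts at week 12 (assumption), three visits can register a recurrence: 26, 38 and 52. If it starts at a first response at week 2 (assumption), six can: 4, 8, 12, 26, 38 and 52. The plan does not say which applies.

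**The case against.** The strongest reply is that this is a rough translation and the criterion may be workable in the original. Item 8 also expresses percentage change in HRSD-17 against baseline. A rise in points exceeding 30% of baseline fits that usage and counts every return to entry severity. This is a fair account of what may have been intended. It does not rescue the text, which states a rise compared with the baseline and does not mention the response score as the starting point.

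A second reply is that the three routes are alternatives, so a patient back at entry severity can still count through a DSM-IV episode or readmission. That stands, and it limits the consequence to the score route.

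Several stronger readings are tempting, but the documents do not support them:

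- **That the plan gives no reference score.** It names one, the baseline. The trouble is that this reference sits badly with a rule that applies only after a fall of at least 50%.
- **That item 9 and the secondary endpoint analysis contradict each other.** Item 9 restricts the comparison to patients who have responded or remitted. The analysis section speaks of the whole study period, which is broader but compatible, since maintenance falls within the study. What is missing is a statement of the risk set and clock.
- **That DSM-IV relapse would go undetected.** The per-visit list, "At each visit, the scale evaluation (cognitive function, psychosocial function evaluation), the level of Alzheimer associated neurofilament protein" and what follows it, names no diagnostic reassessment. But the investigator reviews results and adjusts treatment at each visit, and silence in a brief plan does not show that a diagnosis would not be made.
- **That a known number of relapses would be missed.** The documents give nothing from which to estimate one.

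**Conclusion.** The point holds for the score route of item 9. As written, it requires at least 24, 32 or 40 points for baselines of 18, 24 or 30, and it never registers a full return to entry severity. For baseline 18 with response at 9, the lowest qualifying score is 24, 12 or 15 depending on the reading, so the event count depends on the reading. The missing time origin and maintenance start are gaps in detail that belong in the same edit.

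The conclusion rests on taking the baseline to mean the entry score, the only HRSD-17 baseline described. Confidence is moderate because the text is translated.

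The reach is one secondary endpoint. The primary ADAS-cog comparison and the sample size are untouched, and items 2, 7 and 8 still report HRSD-17 change, remission and response by visit. The definition should be corrected, but the trial's main conclusion does not depend on it.

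**What to change.** Restate the score route in item 9 with an explicit reference score suited to a rule that applies only after response. The wording should meet two conditions: a responder who returns to entry severity is counted, and no patient is in response or remission and in recurrence at the same visit. The reference and the cut-off are for the sponsor to choose.

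In the same edit, state in the secondary endpoint analysis that the Kaplan-Meier and Cox risk set for recurrence is the responders or remitters of item 9. Give the time origin, and define the start of the maintenance treatment period, a term that appears only in item 9.

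The cost is one reworded definition and two or three sentences. No visits or ratings are added, because HRSD-17 is already scheduled at every follow-up. The downside is that recurrence rates will look higher than under the literal wording.

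### The between-arm recurrence comparison is limited to patients who have responded or remitted, yet it is read as an intervention effect; if response rates differ, it can be biased against the better arm.

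*Combined protocol and SAP*

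**What the plan says.** **Endpoint (Efficacy index, Secondary efficacy indicators, item 9).** Recurrence is any one of three conditions:
- a diagnostic criterion: "the subject meets the DSM-IV diagnostic criteria for depressive episode";
- a re-admission criterion: "The subject was hospitalized again due to depression";
- a score criterion, applied once HAMD-17 has fallen by at least 50%: "ham-d17 score increased by more than 30% compared with the baseline at any visit point".

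The item closes by setting the comparison in the maintenance period: "after the treatment of the subjects is effective or remission, the proportion of relapse and the time of relapse between the two groups".

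**Analysis (Statistical analysis methods, Secondary endpoint analysis).** The comparison of curves is worded as "recurrence rate and other outcome indicators during the study period were compared between groups using the Kaplan-Meier curve". The effect estimate is model-based: "the COX proportional hazards model was used to evaluate the impact of the intervention". Confounders are to be controlled for, with disease duration as the example given.

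**Analysis set (Statistical analysis methods).** The FAS is all randomised cases with a valid baseline. "Secondary efficacy measures were analyzed using only FAS without carry-over".

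**Entry state (Research object, Inclusion criteria, item 4).** "Currently in the acute phase, the total score of hrds-17 at baseline is ≥ 18 points".

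Remission and response are also compared between arms in their own right, as secondary indicators 7 and 8. The documents do not state time zero for recurrence, who is in the risk set, when the maintenance period starts, or how a patient who never responds is handled.

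**The concern.** Randomisation makes the arms comparable at baseline. It does not make the responders in one arm comparable with the responders in the other, because treatment may change who responds. Suppose training helps some harder-to-treat patients respond. They then enter the group in which relapse is counted, while similar patients in the control arm stay outside it. A Cox estimate from such data mixes two things: the effect on relapse, and the effect on who becomes eligible to relapse. The plan words this estimate as the impact of the intervention and carries no caveat.

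A response difference is not remote. The project basis and the research status section cite work in which training relieved depressive symptoms as well as cognition. At stake is the reading of one secondary endpoint: training could appear to raise recurrence, or fail to lower it, because more patients improved.

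**Working it through.** **1. The plan's own figures.** The only calculated figure is the primary sample size. With a difference of 2.2, SD 4, one-sided α = 0.025 and 80% power, n = 2 × (4 × (1.960 + 0.842) / 2.2)² = 51.9 per arm. This rounds to 52, against 51 stated. Then 51 / 0.80 = 63.75, so 64 per arm. (This reproduction leaves out the stated superiority limit of 3, which is a separate matter.) Nothing is calculated for recurrence, so only the 64 per arm is carried forward. All response and relapse rates below are assumptions.

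**2. Is the comparison really conditional on response?** Only the third criterion states a prior response. The DSM-IV and re-hospitalisation criteria do not. Two things still support the conditional reading. The closing clause of item 9 sets the comparison after response or remission. And every patient enters in an acute episode, so a DSM-IV episode criterion with no condition attached would already be met at baseline.

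**3. Reading A: FAS, with never-responders kept as event-free.** Recurrence proportion = response rate × relapse risk among responders. Assume response of 60% (training) and 40% (control), with the same 30% relapse risk in every responder.
- Training: 0.60 × 0.30 = 0.18, about 12 of 64.
- Control: 0.40 × 0.30 = 0.12, about 8 of 64.
- Ratio: 0.18 / 0.12 = 1.5 against the arm with more responders, with no difference in anyone's risk.

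A smaller response gap gives a smaller distortion. With 20% relapse among responders and a constant-hazard approximation, HR = ln(1 − p_training) / ln(1 − p_control):
- response 60% v 50%: recurrence 12% v 10%, HR 1.21;
- response 70% v 50%: recurrence 14% v 10%, HR 1.43.

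**4. Reading B: responders only.** Keep 60% v 40% response. Suppose the 40% who would respond in either arm have a 30% relapse risk, and the extra 20% who respond only with training have a 45% risk.
- Training: (0.40 × 0.30 + 0.20 × 0.45) / 0.60 = 0.21 / 0.60 = 35%.
- Control: 30%.

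Training has raised no one's risk; the mix of responders differs.

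A large simulation (50,000 per arm) let a latent severity drive both response and relapse, with no effect of training on relapse in any patient. Cox hazard ratios among responders were:

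| Response, control v training | Severity unrelated to relapse | Severity related to relapse (two strengths) |
|---|---|---|
| about 50% v 50% | 0.97 | 0.99–1.01 |
| about 50% v 61% | 1.02 | 1.10–1.17 |
| about 50% v 70% | 0.97 | 1.22–1.38 |

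Reading B therefore needs two conditions: different response rates, and extra responders whose relapse risk differs. If the extra responders were at lower risk, the bias would go the other way.

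**5. An all-randomised endpoint on the same assumptions.** Responded and recurrence-free = response rate × (1 − relapse risk).
- Step 3 rates (60% v 40%): 0.60 × 0.70 = 42% v 0.40 × 0.70 = 28%.
- Step 4 rates: 0.60 × 0.65 = 39% v 28%.

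This endpoint favours the arm that did better, while the recurrence comparison goes against it.

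**The case against.** **The recurrence definition is unsettled.** A reader might infer that a non-responder can never recur. The criteria do not say so. Two of the three carry no response condition, and a non-responder who is re-hospitalised could be counted as an event. That would tend to count against the arm with fewer responders. This stands as a limit: Reading A depends on the closing clause of item 9. It also strengthens the case for stating the risk set.

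**Much of the remedy exists.** Indicators 7 and 8 already compare remission and response at each visit in the FAS, and HRSD-17 change is analysed at every follow-up. A patient who has lost response by week 52 is no longer a responder there. The overlap is real but partial. Indicator 8 does not use the DSM-IV or re-hospitalisation criteria, and a patient who relapsed and recovered again would count as a responder.

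**A reader might infer that the trial's claim of benefit over 52 weeks rests on recurrence.** The documents do not support that. The aim is cognition, the primary endpoint is ADAS-cog at week 12, and longer-term cognition has its own indicator (item 1).

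**The illustration is generous.** Both arms receive SSRIs under the same adjustment rules, and nothing in the plan assumes a 20-point response gap. With a gap of about 11 points, the simulated responder-only hazard ratio is only 1.10–1.17. Even 12 v 8 events of 64 gives a Fisher p-value of 0.47, so a nominally significant false signal of harm is unlikely at this size. This stands. The concern is a distorted estimate presented as an intervention effect, not a predicted significant result.

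**Conclusion.** The concern holds as a defect in one secondary endpoint. As written, item 9 conditions the comparison on response or remission, while the analysis section treats the result as the impact of the intervention in a FAS-only plan. If response rates differ between arms, that comparison can be biased against the better arm. Under the FAS reading this needs only a response difference and never-responders counted as event-free. Under the responder-only reading it also needs a different relapse risk in the extra responders. Adjusting for disease duration or similar factors concedes possible confounding but does not restore randomisation.

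The size and direction in this trial are unknown, because the documents give no response or relapse rates; 18% v 12% is an illustration only. It would go too far to say that training will look worse, or that recurrence is impossible in non-responders. The primary endpoint is unaffected. The change should be made, but the trial does not stand or fall on it.

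**What to change.** 1. **Between-arm comparison.** Use an all-randomised endpoint from data already collected: responded and recurrence-free at week 52, compared as a proportion in the FAS. Never responding, or recurring, counts as not achieved. Weeks 26 and 38 are supportive, so that three time points do not become three unranked tests.
2. **Missing status.** Report it both as failure and by available cases or another stated method. With 20% loss planned for, failure as the sole rule would let dropout drive the result.
3. **Definition.** State whether the DSM-IV and re-hospitalisation criteria require a prior response or remission, and when the maintenance period begins. The new endpoint depends on this.
4. **Responder-only Kaplan-Meier and Cox.** Keep them, with time zero and the risk set stated. Label them descriptive and non-randomised, and drop the wording that presents the Cox estimate as the intervention's impact.

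**Cost.** SAP wording, a settled recurrence definition and one extra table; no new visits or measurements. The new endpoint combines response with durability and partly overlaps indicator 8, and the responder-only test loses its causal reading.
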